The vagus nerve plays a key role in regulation of nausea and vomiting, and there is evidence of vagus afferent effects on nociception, which suggests that electrical stimulation modulates nauseas and vomiting. The current proof of concept study explores the possibility that non-invasive vagus nerve stimulation (nVNS) could have clinical effects similar those of an implanted gastric electrical stimulation device in patients with symptoms of gastroparesis. GES report some complications, the main one being the infections of subcutaneous pocket, inflammation over implant site, device migration/erosion, lead penetration, extra-abdominal pain, seroma and hematoma. Less common complications include erosions of the abdominal wall by the device, penetration of the leads through the gastric wall, or tangling of wires in the generator pocket and formation of adhesions. GES is relatively expensive treatment with the high cost of the device and for the surgical procedure. ²⁰⁻²²

gammaCore (nVNS) is the first non-invasive, handheld medical device²³ applied on the side of the neck and sends gentle, patented mild electrical stimulation through the skin to activate the vagus nerve. nVNS offers a potential alternative to GES that could eliminate significant risks of injury or illness or identify likely responders to implantable neurostimulator including implanted VNS (iVNS). nVNS could provide a more effective and safer alternative to the use of traditional rescue medications.

nVNS primarily stimulates myelinated sensory afferent vagus nerve fibers as they ascend through the neck in the carotid sheath. nVNS has been cleared for the acute and preventive treatment of migraine and the acute and preventive treatment of cluster headache by the Food and Drug Administration (FDA) and is also CE marked and used in several all forms of primary headache. ^{24, 25}

The hypothesis of the pilot study is that nVNS will result in relief of nausea by modulation of vagal nerve activity.

- **2. Objectives** (include all primary and secondary objectives)
- The principal objective of this open label pilot study is to evaluate whether acute treatment
 of nausea exacerbations with nVNS will be effective in reducing the use of rescue
 medications.
- Secondary objectives of this study include:
 - o Determine the nature and incidence of adverse effects.

- Exploratory objectives
 - o Determination of the effects of nVNS (or correlation with response) use on:

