 - Patient Assessment of Upper Gastrointestinal Symptom Severity Index (PAGI-SYM) and the Gastrointestinal Symptom Rating Scale (GSRS).
 - Depression and anxiety using the Beck Depression Inventory and State-Trait Anxiety Scores.
 - Frequency of migraines and headaches (since many patients with gastroparesis have concomitant migraine) defined as, 'migraine day'= a migraine headache occurring in a 24-hour period, and a 'headache day'= any headache occurring in a single calendar day.
 - Autonomic symptoms as determined by the COMPASS-31 score.
- **3. Background** (briefly describe pre-clinical and clinical data, current experience with procedures, drug or device, and any other relevant information to justify the research)

Chronic nausea and vomiting are the clinical hallmarks of gastroparesis and Chronic Unexplained Nausea and Vomiting or CUNV (very similar to Functional Dyspepsia of the postprandial subtype, FD-PPS, by Rome criteria) or related disorders and in most cases, are constant and daily symptoms. However, in addition, the majority of these patients also experience periodic exacerbations of these symptoms either on a daily basis or several times in a week. These exacerbations require them to use "rescue" medications such as 5-HT3 antagonists (e.g. ondansetron) or D2 receptor antagonists (e.g. Promethazine). These are only partially effective at best and often associated with adverse effects. Our hypothesis is that nVNS may provide a more effective and safer alternative to the use of traditional rescue medications. We therefore believe that while nVNS may not necessarily be a stand-alone treatment for gastroparesis, it has the potential for meeting a large unmet "niche" need in this condition.

4. Study Procedures

Patients who appear to be eligible after chart review and completion of standard of care tests and procedures for gastroparesis, CUNV or related disorders will be invited to undergo screening for study. Patients considered by the clinical center investigator as likely to be eligible for participation in the trial may be consented, registered and screened at a visit that is part of the ongoing clinical care of the patient.

After informed consent is obtained, patients will fill out a validated symptom-based questionnaires and assessment daily.

Visit schedule

- At least 2 weeks of pre-treatment observation (screening).
- 8 weeks of treatment
- 2 weeks of post-treatment observation.
- Length of recruitment: 9 months

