 - Gastroparesis Cardinal Symptom Index Daily Diary (GCSI-DD)
 - Rescue medication uses daily diary- number of pills and type
 - Migraine and headache daily diary
 - Gastrointestinal Symptom Rating Scale (GSRS)
 - Patient Assessment of Upper Gastrointestinal Symptom Severity Index (PAGI-SYM)
 - Beck Depression Inventory (BDI-II)
 - State- Trait Anxiety Inventory (STAI)
 - Average weekly frequency of migraine for the last 4 week period
 - COMPASS-31 score.
 - Global patient impression (GCPI) questionnaire.

Laboratory test results that need to be collected are EKG and urine pregnancy test. Review study of adverse events will be addressed.

- Week 8 visit: This will be the end of study visit. A medical history, including side effect or symptom profile will be collected. The following questionnaires should be completed and collected:
 - Gastroparesis Cardinal Symptom Index Daily Diary (GCSI-DD)
 - Rescue medication uses daily diary- number of pills and type
 - Migraine and headache daily diary
 - Gastrointestinal Symptom Rating Scale (GSRS)
 - Patient Assessment of Upper Gastrointestinal Symptom Severity Index (PAGI-SYM)
 - Beck Depression Inventory (BDI-II)
 - State- Trait Anxiety Inventory (STAI)
 - COMPASS-31 score.
 - Global patient impression (GCPI) questionnaire.
- Week 10 visit: This will be the end of study visit. A medical history, including side effect or symptom profile will be collected. The following questionnaires should be completed and collected:
 - Gastroparesis Cardinal Symptom Index Daily Diary (GCSI-DD)
 - Rescue medication uses daily diary- number of pills and type
 - Migraine and headache daily diary
 - Gastrointestinal Symptom Rating Scale (GSRS)
 - Patient Assessment of Upper Gastrointestinal Symptom Severity Index (PAGI-SYM)
 - Beck Depression Inventory (BDI-II)
 - State- Trait Anxiety Inventory (STAI)
 - COMPASS-31 score.
 - Global patient impression (GCPI) questionnaire.

	Screening & GammaCore treatment Visits (Weeks)		Follow-up Visits: Weeks from start of treatment		
	Screening (0)	Treatment initiation (2)	4	8	10
Consent	X				
Baseline medical	X				
history					
GCSI-DD	X		X	X	X
Rescue Medication Daily Diary	X		X	X	X
Migraine and Headache Daily Diary	X		X	X	X
Collection of GCSI- DD		X	X	X	X
Collection of Rescue Medication Daily Diary		X	X	X	X
Collection of Migraine and Headache Daily Diary		X	X	X	X
PAGI-SYM questionnaire	X		X	X	X
GSRS questionnaire	X		X	X	X
Beck Depression Inventory-II	X		X X	X X	X X

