State Trait Anxiety Inventory	X		X	X	X
COMPASS 31-score			X	X	X
Noninvasive Vagal Neural Stimulation (VNS) device dispensed		X			
Follow-up medical history, including review of adverse events			X		X
12-lead EKG	X		X		
Urine pregnancy test	X		X		

Specific Tests and Questionnaires

- Pregnancy test: Women of childbearing potential must have a negative urine pregnancy test.
- 12-lead EKG: To rule out any abnormal baseline electrocardiogram such as second and third degree heart block, atrial fibrillation, atrial flutter, recent history of ventricular tachycardia or ventricular fibrillation, or clinically significant premature ventricular contraction, history of prolonged QT interval or a history of clinically significant arrhythmia.
- Gastroparesis Cardinal Symptom Index (GCSI) Daily Diary:²⁶ Consists of five core symptoms (nausea, vomiting, early satiety, postprandial fullness, upper abdominal pain).
 Each night, participants grade the severity of symptoms over the prior 24 hours. The GCSI-DD core symptom composite score (an average of the five core symptoms) is designed to detect clinical improvement in symptoms of gastroparesis and to be used as a PRO outcome for clinical trials.
- Rescue medication daily diary: Must contain the name of the antiemetic medications, dosage, frequency and number of pills during the day.
- Gastrointestinal Symptom Rating Scale (GSRS): ²⁷ The GSRS is a disease-specific instrument of 15 items combined into five symptom clusters depicting Reflux, Abdominal pain, Indigestion, Diarrhea, and Constipation. The GSRS has a seven-point graded Likert-type scale where 1 represents the absence of troublesome symptoms and 7 represents very troublesome symptoms. The reliability and validity of the GSRS are well-documented and normative values for a general population are available.
- Patient Assessment of Upper Gastrointestinal Disorders-Symptoms (PAGI-SYM): ²⁸ The self-reported questionnaire is composed of 20 items and 6 subscales. The severity of each symptom item over a 2-week recall period is scored from 0 (none or absent) to 5 (very severe). The GCSI, a 9-symptom survey relevant to gastroparesis stratified in 3 subscales nausea/vomiting, fullness/early satiety, and bloating, is contained in the PAGI-SYM. The GCSI correlates with patient severity ratings and is responsive to changes in overall symptoms. Two additional items for constipation and diarrhea also will be recorded and scored and their main symptom will be determined.

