The questionnaires will also be filled out during the treatment and during the 2 weeks after nVNS treatment has been completed. All questionnaires are short and easy to fill out with multiple-choice type responses. Adverse events (AEs) will also diarized.

All participants who sign the ICF will be registered in the trial database. Each participant who starts screening must be accounted for at the end of the screening, as either a screening success or a screening failure. A screening failure is defined and a participant who signed the consent form and was registered in the nVNS trial data system, but is found to be ineligible prior to start of treatment; screening failures include patients who meet medical eligibility criteria but change their mind and do not consent to participate in the trial. The reason for screening failure will be recorded and keyed into the trial database.

5. Inclusion/Exclusion Criteria

Inclusion criteria

- Age 15 years or older at registration.
- Diagnosis of gastroparesis as documented by gastric emptying scintigraphy (4-hour emptying after a low-fat meal with any combination of 2- and 4-hour retention of >60% and 10%, respectively), or Chronic Unexplained Nausea and Vomiting (CUNV).
- Ongoing symptoms (i.e. Nausea and vomiting, bloating, and abdominal pain) with a nausea score of 3 or more on the PAGI-SYM scale at baseline (moderate to severe nausea).
- Exclusion of other causes of symptoms such as mechanical gastrointestinal obstruction, uncontrolled esophagitis, peptic ulcer disease, etc. By standard radiographic or endoscopic tests.
- Use of the following medications on an as-needed basis: ondansetron, promethazine or prochlorperazine but no more than four times a day.

Exclusion criteria

- Another active disorder, which could explain symptoms in the opinion of the investigator.
- Age < than 15 years.
- Pregnancy or nursing.
- A previous surgery of the upper gastrointestinal tract, including vagotomy.
- Use of narcotics more than 3 days per week.
- History of prolonged QT interval or a history of clinically significant arrhythmia.
- Abnormal baseline ECG (e.g. Second- and third-degree heart block, atrial fibrillation, atrial flutter, recent history of ventricular tachycardia or ventricular fibrillation, or clinically significant premature ventricular contraction).
- Previous bilateral or right cervical vagotomy.
- Uncontrolled high blood pressure.

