- Total of 45 patients. This is a pilot study to assess the strength of the signal (improvement) with peripheral VNS for nausea. Since there is evidence that the left and right vagus may have different pathways within the CNS, with the left side being dominant in innervation of center involved in food aversion and nausea (Cell 175, 665–678, 2018), we are proposing to study three groups as follows
 - Group 1; Start with left sided stimulation 15 patients
 - Group 2. Start with right sided stimulation 15 patients
 - Group 3. Both sided stimulation 15 patients
- Our assumptions are as follows, in terms of the number of patients improving in each group

Group 1: 4/15 Group 2: 11/15 Group 3: 7/15

If these assumptions are true, the type I error will be < 0.05

8. Risks³²⁻³⁴

The adverse reactions observed in nVNS studies include:

- i. Shortness of breath (dyspnea), hoarseness, or change in voice during treatment.
- ii. Muscle twitching, discomfort, or pain during stimulation.
- iii. Change in taste (dysgeusia).

These first three reactions resolved after treatment was completed.

- iv. Local skin irritation/inflammation.
- v. Any progression of headache symptoms.

Adverse reactions not seen in the studies, but associated with implanted vagal nerve stimulation devices include:

- vi. Tingling, pricking, or a feeling of "pins and needles" on the skin where the device is applied (paresthesia or dysaesthesia) lasting beyond the treatment period.
- vii. Fainting (syncope), light-headedness, and/or dizziness.
- viii. Sweating.
- ix. Fatigue, depressed mood.
- x. Tinnitus.
- xi. Diarrhea.
- xii. Abnormal heart rhythm.

Adverse events will be evaluated in every follow-up visit. A form of Adverse Event will be completed if the candidate complains of any symptoms, sign, abnormal assessment or any combination of these. An adverse event can be expected side effect that is of a serious nature, or an unexpected side effect/event regardless of severity.

This study will monitor and report adverse events to ensure patient safety to IRB and FDA. Signs and symptoms associated with the adverse event will be graded as to severity by the clinical site staff as mild, moderate, or sever using Version 5.0 of the National Cancer Institute's Common Terminology Criteria for Adverse Events (CTCAE).

9. Benefits

Description of the probable benefits for the participant and for society.

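### Adverse-effect incidence has no new-or-worsened rule, an AE form trigger that conflicts with the AE definition, and no link to the baseline symptom data already collected

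*Combined protocol and SAP*

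**What the plan says.** Section 2 gives a single secondary objective: "Determine the nature and incidence of adverse effects". The study is open label, and all three groups in section 7 receive stimulation, so there is no sham or untreated comparison.

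Section 8 lists possible reactions. "Any progression of headache symptoms" is among those observed in earlier studies of the device. Dizziness, "Fatigue, depressed mood" and diarrhea are in a second list, known from implanted stimulators but not seen in those studies. Section 2 justifies measuring headache "since many patients with gastroparesis have concomitant migraine".

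On recording, section 8 states: "A form of Adverse Event will be completed if the candidate complains of any symptoms". The sentence goes on to include signs and abnormal assessments. The next sentence is narrower: it admits expected side effects when they are serious, and unexpected ones at any severity. Severity is graded, but no relatedness assessment and no condition that the event be new or worse is stated.

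On timing, the week 4 visit text in section 4 says "Review study of adverse events will be addressed". The table row "Follow-up medical history, including review of adverse events" is marked at weeks 4 and 10 only. The closing paragraphs of section 4 add "Adverse events (AEs) will also diarized", just after a sentence about questionnaires during and after treatment. The screening list contains no AE form or AE diary.

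**The concern.** Without a control group, the patient's own pre-treatment state is the only reference against which an adverse effect can be judged. Several listed reactions are symptoms these patients may have anyway. If any complaint produces an AE form and nothing asks whether it is new or worse, long-standing headache or diarrhea can enter the incidence as if it came from the device. If staff follow the narrower definition instead, a genuine but non-serious worsening of a listed reaction can drop out. The data that could settle the question are collected, but appear in the plan only as exploratory effect measures. The stake is whether the one secondary result can be interpreted. A pre-treatment AE record also cannot be created once treatment has begun.

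**Working it through.** The plan states no AE rate, precision or safety sample size, so there is no figure to reproduce. The check is mainly a comparison of texts.

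**1. Listed reactions that overlap with background illness, against the pre-treatment data in section 4**

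| Reaction (section 8) | Listed from | Pre-treatment record | Used for safety? |
|---|---|---|---|
| Headache progression | studies of this device | daily headache diary; migraine frequency over 4 weeks (screening and week 4) | not stated |
| Depressed mood | implanted devices | BDI-II | not stated |
| Diarrhea | implanted devices | GSRS diarrhea cluster | not stated |
| Light-headedness, dizziness | implanted devices | COMPASS-31 orthostatic domain: in the screening list, but its screening cell in the table is blank | not stated |

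Heart rhythm also has a screening EKG. No instrument is described as a baseline for fatigue, tinnitus or paresthesia.

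**2. Two test cases under the two sentences of section 8**

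- A patient with migraine mentions her usual, unchanged headache at week 4. Under the form trigger, a form is completed. Under the definition, it counts only if someone judges it a side effect, and no rule for that is given.
- A patient's headaches become moderately worse. Under the form trigger, a form is completed. Under the definition, headache progression is listed and so arguably expected; being non-serious, it is left out.

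The same event is in or out according to the sentence followed, and the error can go either way.

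**3. Timing**

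- First scheduled staff review: week 4, in both the visit text and the table.
- Week 8: blank in the table's AE row; the week 8 visit text asks for a history with side effects; section 8 says AEs are evaluated at every follow-up visit; the opening of the follow-up section names visits only at weeks 4 and 10. These do not agree.
- AE diary: mentioned once. The GCSI-DD, rescue-medication and headache diaries have collection rows; the AE diary has none.

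**4. Scale, for illustration only**

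Assume a share *b* of patients has any headache in a 4-week period regardless of treatment, the device has no effect, and every complaint is counted. Expected patients with an event = n × b, using both sample sizes in the document (45 in section 7, about 30 in section 4):

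- n = 45: 45 × 0.20 = 9; 45 × 0.60 = 27
- n = 30: 30 × 0.20 = 6; 30 × 0.60 = 18

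With an assumed true device rate d = 5%, independent of background b = 20%, the apparent incidence is 1 - (1 - d)(1 - b) = 1 - 0.95 × 0.80 = 24%.

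**5. Unequal windows**

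The run-in is about 2 weeks; follow-up from treatment start is 10 weeks. An event with a constant rate *r* per week is expected 2r times before treatment and 10r times after, a ratio of 10/2 = 5 with no device effect. Raw before-and-after counts would therefore mislead; rates per week would be equal.

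**The case against.** The strongest reply is that the plan is better equipped than this suggests. A reader might infer that nothing is recorded before treatment. That is wrong: the headache diary, BDI-II and GSRS are all taken at screening, and the 4-week migraine frequency is taken at screening and again at week 4, which is a comparable window. A reader might also infer that no adverse event is captured until week 4. The documents support only that the first staff review is then; diary entries could come earlier, and a missing table row is weak evidence against a diary, since the global impression questionnaire is in the visit lists but also has no row. Nor can one say that unvoiced worsening will never be counted: the form trigger includes abnormal assessments, and later visits take a side-effect history.

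The overlap is also partial. Only headache progression comes from studies of this device; dizziness, depressed mood and diarrhea come from implanted devices. Voice change, twitching, taste change and skin irritation are not presented as part of the patients' illness.

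All of this stands and limits the point. It does not supply a new-or-worsened rule, a single AE definition, or any use of the baseline data in the safety summary. A score is not said to become an abnormal assessment at any threshold.

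**Conclusion.** The point holds as a gap in how adverse effects are defined and reported, not as an absence of baseline data. Background symptoms may be counted as adverse effects because no rule prevents it, and listed non-serious reactions may be left out because the definition can be read that way. It would go too far to say that the incidence will be inflated: the direction depends on which sentence staff apply.

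The size cannot be derived from the documents. The 9-27 of 45 (6-18 of 30) figures rest on an assumed background rate and count any headache, whereas the listed reaction is progression; they show only that the distortion could be large for a common symptom. The conclusion itself rests on the text of sections 2, 4 and 8. It should be put right before enrolment.

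**What to change.** 1. Add an AE question to the existing daily electronic diary from the start of screening to week 10, with an issue-and-collect row in the schedule table. This also gives a baseline for reactions that have no instrument, such as fatigue and tinnitus.
2. Reconcile the form trigger with the AE definition in section 8. Report as adverse effects only events that are new or worse than in the screening period, as rates per week because the windows differ. State as a limitation that an intermittent symptom absent by chance from a short run-in can still look new.
3. Tabulate, as safety outcomes, the number of patients worse than baseline by a threshold fixed in advance on the headache diary or 4-week migraine frequency, BDI-II and the GSRS diarrhea cluster. The 4-week migraine frequency is listed only at screening and week 4, so the diary is needed for later visits. Add the COMPASS-31 orthostatic domain once its screening assessment agrees between the screening list and the table.
4. Reconcile AE review at week 8 between the visit text and table in section 4 and the statement in section 8.

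The cost is one diary question, one table row, a few sentences of definition and one tabulation from data already planned. The downside is some pre-treatment event records to process.

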As part of the screening process for the trial, the patient must have a diagnosis of gastroparesis or CUNV with delayed gastric emptying documented by gastric emptying scintigraphy (4-hour emptying after a low-fat meal with any combination of 2- and 4-hour retention of >60% and 10% respectively) and ongoing symptoms such as: nausea, vomiting, abdominal pain, etc. for at least 3 months without any other obvious cause. Patients must also have a normal upper endoscopy or standard radiography, to rule out other potential causes of symptoms such as mechanical obstruction, inflammatory or other structural lesions of the GI tract or non-gastrointestinal causes.

Recording of screening data on trial forms may not start until the patient has signed the informed consent form (ICF). Screening and baseline data collection procedures will include questionnaires, urine pregnancy test, 12 lead EKG, and review of the patient's medical chart.

All participants who sign the ICF will be registered in the trial database. Each participant who starts screening will be accounted for at the end of the screening, as either success or a screening failure. Screening failure is defined as a participant who signed the consent form and was registered in the trial data system, but is found to be ineligible prior to start of treatment. Screening failures include patients who meet medical eligibility criteria but change their mind and do not consent to participate in the trial. The reason for screening failure will be recorded and keyed into the database.

Screening visit:

The patient will undergo a medical history to identify other illness and contraindications for participations such as use of narcotics for more than 3 days per week, previous surgery of the upper gastrointestinal tract, history of prolonged QT interval or clinical significant arrhythmia, etc.

In addition, the patient will be provided with the questionnaires and will be administered on a daily basis for up two weeks before treatment with following questionnaires (delivered electronically):

- Gastroparesis Cardinal Symptom Index Daily Diary (GCSI-DD)

- Rescue medication uses daily diary- number of pills and type. Rescue medications that will be allowed for this trial are ondansetron, promethazine and prochlorperazine.
- Migraine and headache daily diary
- Gastrointestinal Symptom Rating Scale (GSRS)
- Patient Assessment of Upper Gastrointestinal Symptom Severity Index (PAGI-SYM)
- Beck Depression Inventory (BDI-II)

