- Currently implanted with an electrical and/or neurostimulator device, including but not limited to cardiac pacemaker or defibrillator, vagal neurostimulator, deep brain stimulator, spinal stimulator, bone growth stimulator, or cochlear implant.
- History of carotid endarterectomy or vascular neck surgery on the right side.
- Implanted with metal cervical spine hardware or has a metallic implant near the gammaCore stimulation site.
- Any other condition, which in the opinion of the investigator would impede compliance or hinder the completion of the study.
- Failure to give informed consent.

6. **Drugs/ Substances/ Devices**

gammaCore Sapphire (nVNS) ²³⁻²⁵

Description:

nVNS is a multi-use, hand-held, rechargeable, portable device consisting of a rechargeable battery, signal-generating and -amplifying electronics, and a control button for the patient to control the signal amplitude. The device provides visible (display) and audible (beep) feedback on the device and stimulation status. A pair of stainless steel surfaces, which are the skin contact surfaces ("stimulation surfaces"), allow the delivery of a proprietary electrical signal. The patient applies electroCore-approved gel to the stimulation surfaces to maintain an uninterrupted conductive path from the stimulation surfaces to the skin on the neck. Tubes of electroCore-approved gel are provided with each unit and refill kit for this purpose. The stimulation surfaces are capped when not in use.

7. Study Statistics

Data analysis will be performed at Mayo Clinic Scottsdale, Arizona by [name], ([contact]). This site will no recruit participants.

Johns Hopkins will serve as coordinating center, responsible for overall data management, monitoring and communication among both sites, and general oversight of the conduct of this protocol.

Outcome measures

Primary: The primary outcome measure is the average daily use of rescue medications for exacerbation of nausea/vomiting.

Sample size justification

- Primary endpoint: Improvement in nausea control, as defined by a 50% reduction n the number of weekly doses of rescue medications, compared with baseline.

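### PAGI-SYM nausea is both an entry criterion and an exploratory outcome with no defined baseline; if the qualifying score is the baseline, a fall is expected with no treatment effect

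*Combined protocol and SAP*

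**What the plan says.** Section 5 (Inclusion criteria) admits patients with ongoing symptoms "with a nausea score of 3 or more on the PAGI-SYM scale at baseline". Section 4 (Specific Tests and Questionnaires) describes PAGI-SYM as 20 items in 6 subscales, each item scored 0 to 5 over a two-week recall period.

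PAGI-SYM is also an outcome. It is the first entry in the exploratory list of Section 2, introduced by "Determination of the effects of nVNS (or correlation with response) use on". The primary outcome lies elsewhere: in Section 7, "The primary outcome measure is the average daily use of rescue medications for exacerbation of nausea/vomiting", with a responder defined by a halving of weekly rescue doses.

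The documents give two accounts of when PAGI-SYM is taken before treatment:

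- In the visit schedule table, the row "PAGI-SYM questionnaire" is marked at Screening (0), blank at Treatment initiation (2), and marked again at weeks 4, 8 and 10.
- In the screening-visit text of Section 4, PAGI-SYM is in the list that "will be administered on a daily basis for up two weeks before treatment with following questionnaires (delivered electronically").

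No section states which record decides eligibility, which is the baseline for PAGI-SYM change, or how that change is analysed. The study is open label and all three groups in Section 7 are stimulated; no sham or untreated group is described.

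**The concern.** When patients are admitted because a noisy score is high, part of that height is chance, and the next score tends to be lower whatever is done in between. If change is measured from the qualifying score, the fall is counted as improvement. The error always favours the device, and without an untreated group the data cannot separate it from a treatment effect.

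The entry criterion itself uses the word baseline for the qualifying score, and the schedule table offers no later pre-treatment PAGI-SYM. An analyst following the table would therefore very likely use the screening score for both purposes. At stake is how far the reported fall in PAGI-SYM nausea can be trusted when the pilot's exploratory results are used to plan later work.

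**Working it through.** **Plan's own figure.** There is none for PAGI-SYM. The only statistical figure, in Section 7, is an error rate below 0.05 for assumed improvers of 4/15, 11/15 and 7/15. It concerns rescue-dose response. As the p-value of that table it reproduces (Pearson chi-square 6.58 on 2 df, p = 0.037; exact p = 0.046), but it has no bearing on this point.

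**Inputs from the documents.** Cut-off 3 on a 0-5 item (reading the entry score as the nausea item); two-week recall; about 30 patients (Section 4) or 45 (Section 7).

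**Assumed inputs, not in the documents.** Screened-population mean 2.5 to 3.5, SD 1.0 to 1.3, test-retest correlation r 0.5 to 0.9.

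**Formula.** For a normal score selected at 3 or more, with no treatment effect:

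expected fall = (1 − r) × SD × φ(a) / (1 − Φ(a)), where a = (3 − mean)/SD.

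Worked case, mean 2.5, SD 1.3, r 0.7: a = 0.5/1.3 = 0.385. The mean among those selected is 3.88, which is 1.38 above the population mean. The fall is 0.3 × 1.38 = 0.41.

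| Mean | SD | r = 0.5 | r = 0.7 | r = 0.9 |
|---|---|---|---|---|
| 2.5 | 1.0 | 0.57 | 0.34 | 0.11 |
| 2.5 | 1.3 | 0.69 | 0.41 | 0.14 |
| 3.0 | 1.0 | 0.40 | 0.24 | 0.08 |
| 3.0 | 1.3 | 0.52 | 0.31 | 0.10 |
| 3.5 | 1.0 | 0.25 | 0.15 | 0.05 |
| 3.5 | 1.3 | 0.37 | 0.22 | 0.07 |

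**Check on a bounded, rounded item.** A simulation of 1,000,000 draws, rounded and clipped to 0-5, with SD 1.3 and no effect, gives falls of 0.07 to 0.57. The central case (mean 3.0, r 0.7) gives 0.26, against 0.31 by formula. The plan names no test for PAGI-SYM. For illustration, a two-sided 5% paired t-test would show a false improvement in 9% to 72% of trials at n = 30 (central case 29%) and 12% to 88% at n = 45 (central case 42%).

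**Spread to wider scores.** If only the nausea item regresses, the 20-item mean shifts by 0.07/20 to 0.57/20, about 0.004 to 0.03 points. Section 4 says the 9 GCSI symptoms within PAGI-SYM form 3 subscales. If each has 3 items (an assumption), the nausea/vomiting subscale shifts by 0.07/3 to 0.57/3, about 0.02 to 0.19. Both shifts are larger if errors in other items correlate with the error in nausea.

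**Would daily scores help?** With a 14-day recall, a score taken d days after the qualifying one shares 14 − d of its 14 days: 7 of 14 after one week. Such scores carry much of the same error and do not by themselves remove the bias.

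**Separate baseline.** When change is measured from a second pre-treatment score not used for selection, the simulated no-effect change lies between −0.002 and +0.002 in every scenario. This assumes independent errors, which requires recall windows that do not overlap.

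**The case against.** The strongest objection is that the screening score cannot be called the only baseline. That reading follows the schedule table but ignores the Section 4 screening text, under which PAGI-SYM is given daily before treatment. This stands: what the documents show is a conflict and an undefined baseline. It does not remove the problem, because overlapping daily scores share error with the qualifying score.

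A reader might also infer that improvement is built into PAGI-SYM as a whole. The documents do not support that. The cut-off is on nausea, one part of a 20-item instrument, and the total moves little unless item errors correlate.

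A reader might infer further that the pilot's signal is compromised. The remark about signal strength sits in the sample-size justification of Section 7, where the endpoint is "Improvement in nausea control, as defined by a 50% reduction n the number of weekly doses of rescue medications, compared with baseline". PAGI-SYM is exploratory, with no threshold or decision attached. Entry caps as-needed rescue use but sets no minimum, so selection on nausea reaches the primary outcome only through its correlation with nausea.

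The size is assumed and may be small. Candidates are pre-screened by chart review as likely to be eligible, and Section 3 describes symptoms that are mostly constant, so a high mean and a high r are plausible; the low end of 0.05 is close to nil. The formula also ignores the scale's upper bound: at mean 2.5 and SD 1.3, about 8% of selected patients would score above 5. The bounded simulation is lower for that reason.

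Finally, expectation and natural fluctuation affect every symptom score in an open-label before-after study, and regression should be similar across the three stimulated groups. Both are true. They limit the importance of the point, but the before-after fall in nausea remains biased.

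**Conclusion.** The point holds as a conditional one. The documents conflict on how often PAGI-SYM is taken before treatment and never define the baseline for change. If that baseline is the qualifying score, or a score whose recall overlaps it, the nausea item and nausea/vomiting subscale are expected to fall with no treatment effect. The direction is certain for any test-retest correlation below 1. The size, about 0.05 to 0.69 points on the 0-5 item, rests wholly on the assumed mean, SD and correlation.

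The consequence is confined to before-after change in an exploratory nausea score. It gives no ground for saying that the primary outcome, the PAGI-SYM total or comparisons between comparable groups are materially biased by this mechanism. It is a minor point, worth acting on because the remedy is cheap.

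**What to change.** 1. Reconcile the schedule table with the screening text of Section 4 on when PAGI-SYM is completed before treatment, and state which record decides eligibility and which is the baseline for change.
2. Use the screening PAGI-SYM for eligibility only. Repeat it at treatment initiation and take that score as the baseline, without re-applying the cut-off, since doing so would bring the selection back.
3. Keep the two scores at least two weeks apart so that their recall windows do not overlap. The table's week 0 and week 2 columns and the visit schedule's two-week minimum observation period allow this. The screening text sets two weeks as a maximum and must be aligned. If symptom flares outlast the gap, some regression will remain.
4. Also report nausea change from the run-in average of the GCSI-DD nausea item. It is already collected, asks about the previous 24 hours and is not the selection variable.

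The cost is one extra 20-item electronic questionnaire at an existing visit; item 4 needs no new data. If the repeat is not adopted, at least define the baseline and report PAGI-SYM nausea change as descriptive, with this limitation stated.
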